4.4. End of Study Definition

A participant is considered to have completed the study if he/she has completed ***all phases for a given Part*** (ie, 1, 2, or 3) of the study, including the last scheduled procedure shown in the [SoA-Table A](#), [SoA-Table B](#), and [SoA-Table D](#).

The end of the study is defined as the date of the last visit of the last participant in the study, globally.

5. STUDY POPULATION

This study can fulfill its objectives only if appropriate participants are enrolled. The following eligibility criteria are designed to select participants for whom participation in the study is considered appropriate. All relevant medical and nonmedical conditions should be taken into consideration when deciding whether a particular participant is suitable for this protocol.

Prospective approval of protocol deviations to recruitment and enrollment criteria, also known as protocol waivers or exemptions, is not permitted.

5.1. Inclusion Criteria

Participants are eligible to be included in the study only if **all** of the following criteria apply:

Age and Sex:

1. ***In Part 1 and Part 3***, male and female participants must be 18 to 55 years of age, inclusive, at the time of signing the ICD:
 - ***In Part 2***, the upper limit of acceptable age will be extended to 65 years, inclusive, at the time of signing the ICD;

- Refer to [Section 10.4](#) for reproductive criteria for male ([Section 10.4.1](#)) and female ([Section 10.4.2](#)) participants.

Type of Participant and Disease Characteristics:

2. Male and female participants who are **healthy** as determined by medical evaluation including medical history, PE, laboratory tests; plus in Part 1 only, cardiac telemetry monitoring.
3. **In Part 2, only**, at Screen and Day -2, meet the following criteria based on assessment via FibroScan®, with a single repeat permitted, on a separate day, to assess eligibility, if needed, at each of these 2 visits:
 - CAP™ ≥ 270 dB/m;
 - VCTE™ < 7.0 kPa.
4. Participants who are willing and able to comply with all scheduled visits, treatment plan, laboratory tests, lifestyle considerations, and other study procedures.

Weight:

5. BMI of ≥ 17.5 and ≤ 30.5 kg/m² and a total body weight > 50 kg (110 lb):
 - **In Part 2**, upper limit of acceptable BMI will be extended up to 35.4 kg/m², inclusive;
 - **In all 3 Parts**, a single repeat assessment of body weight and/or BMI permitted on a different day to assess eligibility, if needed.

Informed Consent:

6. Capable of giving signed informed consent as described in [Section 10.1](#), which includes compliance with the requirements and restrictions listed in the ICD and in this protocol.

5.2. Exclusion Criteria

Participants are excluded from the study if any of the following criteria apply:

Medical Conditions:

1. Evidence or history of clinically significant hematological, renal, endocrine, pulmonary, gastrointestinal, CV, hepatic, psychiatric, neurological, or allergic disease (including drug allergies, but excluding untreated, asymptomatic, seasonal allergies at the time of dosing).

2. Any condition possibly affecting drug absorption (eg, gastrectomy).
3. History of HIV infection, hepatitis B, or hepatitis C; positive testing for HIV, HBsAg, HBcAb, or HCVAb; *though* hepatitis B vaccination (*or* HBsAb positive result) is allowed.
4. Other medical or psychiatric condition including recent (within the past year) or active suicidal ideation/behavior or laboratory abnormality that may increase the risk of study participation or, in the investigator's judgment, make the participant inappropriate for the study.

Prior/Concomitant Therapy:

5. Use of prescription or nonprescription drugs and dietary and herbal supplements within 7 days or 5 -half-lives (whichever is longer) prior to the first dose of study intervention - refer to [Section 6.5](#) for additional details.

Prior/Concurrent Clinical Study Experience:

6. Previous administration with an investigational drug within **30 days** (or as determined by the local requirement) **or 5 half-lives** preceding the first dose of study intervention used in this study (whichever is longer).

Diagnostic Assessments:

7. Results as reported by the sponsor-identified laboratory(ies), **at Screen in all 3 Parts (and Day -2, in Part 2)** as below with a single repeat of **any** of these parameters permitted to assess eligibility, if needed:
 - ALT >ULN (in Part 1 and Part 3) **or** >1.5x ULN (in Part 2, only);
 - AST >ULN (in Part 1 and Part 3) **or** >1.5x ULN (in Part 2, only);
 - ALP >2x ULN;
 - TBili >ULN **and** direct bilirubin >ULN:
 - **Note:** Participants with a history of Gilbert syndrome would be eligible for this study provided direct bilirubin level is \leq ULN, and hemoglobin and reticulocyte count are within the reference range of the sponsor-identified laboratory(ies).
 - Fasting Plasma Glucose >125 mg/dL (6.9 mmol/L);

- Fasting serum TG >150 mg/dL (1.69 mmol/L) – in **Part 1 and Part 2:**
 - Part 3 does *not* include assessment of markers of clinical activity **CCI** [REDACTED] hence no associated exclusionary criteria proposed.
 - eGFR (using serum creatinine and CKD-EPI formulae) of ≤ 90 mL/min/1.73 m² at time of signing ICD;
 - UACR >30 mg/g on spot urine collection;
 - UPCR >200 mg/g on spot urine collection.
- 8. A positive urine drug test for illicit drugs as reported by laboratory, ***at Screen in all 3 Parts (and Day -2, in Part 2, only)***; this single laboratory assessment is ***not*** permitted to be repeated to confirm eligibility.
- 9. Screening supine BP ≥ 140 mm Hg (systolic) or ≥ 90 mm Hg (diastolic), following at least 5 minutes of supine rest. If BP is ≥ 140 mm Hg (systolic) or ≥ 90 mm Hg (diastolic), the BP should be repeated 2 more times and the average of the 3 BP values should be used to determine the participant's eligibility.
- 10. Baseline 12-lead ECG that demonstrates clinically relevant abnormalities that may affect participant safety or interpretation of study results:
 - *Examples include* - baseline QTcF interval >450 msec, complete LBBB, signs of an acute or indeterminate-age myocardial infarction, ST-T interval changes suggestive of myocardial ischemia, second- or third-degree AV block, or serious bradyarrhythmias or tachyarrhythmias;
 - If the baseline uncorrected QT interval is >450 msec, this interval should be rate-corrected using the Fridericia method and the resulting QTcF should be used for decision making and reporting –
 - If QTcF exceeds 450 msec, or QRS exceeds 120 msec, the ECG should be repeated 2 more times and the average of the 3 QTcF or QRS values should be used to determine the participant's eligibility;
 - Computer-interpreted ECGs should be overread by a physician/medical provider experienced in reading ECGs before excluding participants.

Other Exclusions:

11. History of alcohol abuse or binge drinking and/or any other illicit drug use or dependence within 6 months of Screening:
 - Binge drinking is defined as a pattern of 5 (male) and 4 (female) or more alcoholic drinks in about 2 hours;
 - As a general rule, alcohol intake should not exceed 14 units per week (in males) and 7 units per week (in females) – where 1 unit = 8 oz. (240 mL) beer, 1 oz. (30 mL) of 40% spirit, or 3 oz. (90 mL) of wine.
12. Use of tobacco- or nicotine- containing products *in excess* of the equivalent of 5 cigarettes per day or 2 chews of tobacco per day.
13. Blood donation (excluding plasma donations) of approximately 1 pint (500 mL) or more within 60 days prior to dosing.
14. History of sensitivity to heparin or heparin-induced thrombocytopenia *only if* heparin is used to flush IV catheters used during serial blood collections.
15. Unwilling or unable to comply with the lifestyle considerations outlined in [Section 5.3](#).
16. *In Part 2 only*, participants meeting criteria for contraindication to undergoing imaging assessments including –
 - Active placement of medical devices in/on thoracic cavity as these interfere with use of ultrasound-based imaging modalities, and MRI;
 - History/evidence of any of the following:
 - Contraindication to MRI such as ferric implant;
 - History of severe claustrophobia impacting ability to perform MRI during the study even despite mild sedation/treatment with a *short-acting* anxiolytic;
 - Inability to lie still within the *closed* environment of the MRI scanner *or* maintain a breath hold for the required period to acquire images *even despite* mild sedation/treatment with an anxiolytic.
17. Investigator site staff or Pfizer employees directly involved in the conduct of the study, site staff otherwise supervised by the investigator, and their respective family members.

Randomization Criteria – Parts 1, 2, and 3

Participants will be randomized into the study provided they have satisfied **all** the following criteria:

- Eligibility criteria outlined in [Section 5.1](#) and [Section 5.2](#);
- *In addition*, prior to dosing on Day 1, the results of the clinical laboratory tests (including urine drug test) **conducted upon each inpatient admission** must be deemed to have no clinically significant findings, in the opinion of the PI, and as such permit (continued) participation in this study.

In Part 1, participants in the 2 cohorts will be randomized per the scheme summarized in Table 5 with the actual dose administered following the proposed dose-escalation approach outlined in [Section 4.3.3](#) and [Table 3](#).

Table 5. Study C4171001 - Part 1 - Randomization Scheme

Cohort	Sequence	Period ^a			
		1	2	3	4 ^b
1 (n=8)	1 (n=2)	Placebo	Dose 3	Dose 5	Dose 7 ^c
	2 (n=2)	Dose 1	Placebo	Dose 5	Dose 7 ^c
	3 (n=2)	Dose 1	Dose 3	Placebo	Dose 7 ^c
	4 (n=2)	Dose 1	Dose 3	Dose 5	Placebo ^c
2 (n=8)	5 (n=2)	Placebo	Dose 4	Dose 6	Dose 8 ^c
	6 (n=2)	Dose 2	Placebo	Dose 6	Dose 8 ^c
	7 (n=2)	Dose 2	Dose 4	Placebo	Dose 8 ^c
	8 (n=2)	Dose 2	Dose 4	Dose 6	Placebo ^c

- a. In each dose level/Period, the dose being evaluated will be known to the investigator(s) and participants; however, to preserve the double-blind design which participant is receiving PF-07202954 versus placebo will not be known by the investigator(s) and participants.
- b. Pending observed safety/tolerability and plasma PK in previous Periods, an exploratory assessment of plasma PK with dosing following an overnight fast of ≥ 10 hours and/or dosing with high-fat/high-caloric meal (compared to dosing following a standard morning meal in previous Periods) may be considered.
- c. Dose 7 and/or Dose 8 if used to assess plasma PK with dosing in fasted state and/or post high-fat/high-caloric meal – pending observed safety, and PK in previous Periods – will limit the within-participant assessment of food effect to 4 participants on PF-07202954.

In Part 2, participants in each cohort will be randomized to PF-07202954 or placebo in a 4:1 ratio with 10 participants dosed in each cohort.

In Part 3, if conducted, a total of 8 (minimum) to 12 (maximum) participants will be randomized to receive PF-07202954 in the 2 periods – once with a high-fat/high-caloric meal and once following an overnight fast of ≥ 10 hours – with the order randomly assigned.

5.3. Lifestyle Considerations

After confirmation of eligibility at Screen, participants will be instructed to maintain the following guidelines starting prior to **each** inpatient admission **and** for the duration of their participation in the study.

5.3.1. Meals and Dietary Restrictions

While inpatient, the meals consumed are expected to follow the restrictions outlined below with participants encouraged to complete each meal.

- Participants must abstain from all food and drink (except water) –
 - *At least 4 hours* prior to any non-lipid-related safety laboratory evaluations;
 - *At least 10 hours* prior to fasting clinical laboratory evaluations when fasting lipid panel is included.
- Participants will refrain from consuming red wine, grapefruit, or grapefruit -related citrus fruits (eg, Seville oranges, pomelos, fruit juices) from **7 days prior to the first dose** of study intervention until collection of the final PK blood sample.
- Water may be consumed *without restrictions* both prior to *and* after study intervention administration when dosing occurs following a standard morning meal (**or** high-fat/high-caloric meal).
- **Meals in Part 1 and Part 2:**
 - All meals are standard meals **unless** Period 4 in 1 or both cohorts **in Part 1** are used to explore effect of fasted state and/or high-fat/high-caloric meal on plasma PK.
 - On *non-dosing days* while inpatient, as appropriate, standard morning meal, lunch, and evening meal (along with an evening snack) are to be provided at a similar clock time to the clock time when these meals are offered on dosing days:
 - **In Part 2**, on days of **CCI** assessment, time of meal(s) **may** be adjusted to aide scheduling this assessment at the **CCI** facility **while maintaining** the minimum required pre-procedure fast of ≥ 4 hours.
 - The total daily nutritional composition should be **approximately 55% carbohydrate, 30% fat, and 15% protein**:
 - The daily caloric intake per participant should not exceed approximately 3200 kcal;
 - If participants cannot complete the meals, the portion consumed in 25% increments will be documented and potential impact on results assessed by the sponsor study team on a case-by-case basis.

- On dosing days while inpatient:
 - Standard morning meal will be provided following an overnight fast of ≥ 10 hours **and** at approximately 30 minutes prior to dosing at 0 H (**or** similar clock time on non-dosing days), consumed over approximately a 20-minute period (ie, completed approximately 10 minutes prior to dosing);
 - Lunch will be provided approximately 5 hours after morning dosing, at 0H;
 - Evening meal will be provided approximately 12 hours after morning dosing, at 0H;
 - An evening snack may be permitted; however, the need to ensure an overnight fast of ≥ 10 hours is required to enable assessment of clinical laboratory tests the next morning.
- **In Part 1, Period 4 only**, dosing may be altered (refer to [Section 4.2.2](#)) and can occur either following an overnight fast of ≥ 10 hours and/or with a high-fat/high-caloric meal; if this occurs, dosing will occur per the conditions outlined below for Part 3.
- **Meals in Part 3 (if conducted) will be standard *or* high-fat/high-caloric breakfast:**
 - **In both Periods** while inpatient, as appropriate, standard breakfast (*except* Day 1), lunch, and evening meals (along with an evening snack) are to be provided at a similar clock time to when these meals are offered on dosing days;
 - The total daily nutritional composition should be approximately **55% carbohydrate, 30% fat, and 15% protein** – in **both** Periods;
 - **Dosing in Fasted State: On Day 1**, dosing will occur following an overnight fast of ≥ 10 hours with water **only**, with the standard morning meal **not** offered:
 - **When dosing is in the fasted state**, water is permitted until 1 hour prior to dosing and water may be consumed without restriction beginning at 1 hour after dosing.
 - **Dosing in Fed State: On Day 1**, following an overnight fast of ≥ 10 hours, participants should start a **high-fat/high-caloric breakfast** approximately 30 minutes prior to PF-07202954 administration:
 - This breakfast will be consumed over approximately *20-minute interval* and PF-07202954 administered within approximately 10 minutes after completion of the meal at 0H;

- Breakfast will be a high-fat/high-caloric meal consistent with the FDA recommendation for a high-fat/high-caloric meal with a representative example being: 2 eggs fried in butter, 2 strips of bacon, 2 slices of toast with butter, 4 oz. of hash brown potatoes, and 8 oz. of whole milk.
- Lunch will be provided approximately 5 hours after morning dosing at 0H;
- Evening meal will be provided approximately 12 hours after morning dosing;
- An evening snack may be permitted; however, the need to ensure an overnight fast of ≥ 4 hours is required to enable assessment of clinical laboratory tests the next morning.

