2.2.3. Biopharmaceutics

PF-07202954 is a weak base with pKa values of 7.5 and 2.5, thus exhibiting a strong pH-dependent change in solubility. It has high thermodynamic aqueous solubility at physiological pH. The solubility of PF-07202954 in simulated gastric fluid (pH 2.7) and unbuffered water (pH 8) is >27 mg/mL and 0.13 mg/mL, respectively. Solubility in simulated fasted and fed state intestinal fluids (pH 6.9 under both conditions) was observed to be 0.7 mg/mL and 1.2 mg/mL, respectively. Solubility of PF-07202954 is high relative to

the predicted clinical FIH dose range, thus the risk for solubility/dissolution-limited absorption and exposure-limiting precipitation is perceived to be low. Food is expected to have minimal impact on PF-07202954 PK – refer to [Section 4.2.5](#). Preliminary in vitro studies suggest PF-07202954 exhibits moderate in vitro permeability and is a substrate for the intestinal efflux transporters (P-gp and BCRP) that could potentially lead to non-linear plasma PK and high variability in exposure at lower doses.

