6.1.1. Administration

- **Part 1 and Part 2:** following an overnight fast of ≥ 10 hours, participants will receive the study intervention with a standard morning meal at approximately 08:00 hours (± 2 hours):
 - **NOTE:** if **up to 2** of the 8 periods in Part 1 are being utilized to assess plasma PK in the fasted state and/or with high-fat/high-caloric meal, dosing will occur in the appropriate/respective setting (ie, overnight fast of ≥ 10 hours or with high-fat/high-caloric meal).
- **Part 3:** following an overnight fast of ≥ 10 hours, participants will receive the study intervention either with water (fasted state) **or** with a high-fat/high-caloric meal at approximately 08:00 hours (± 2 hours), in each of the 2 Periods, per randomization assignment.

In all cases, investigator site personnel will administer study intervention during each period with ambient temperature water to a total volume of approximately 240 mL;

- Adequate measures to ensure taste masking will be performed **prior to** administration of the study intervention, if needed;
- Additional water (up to 120 mL) **may** be consumed by the participants (eg, extra rinse) in an attempt to ensure that the full dose is consumed – with such instances documented in the source at the site;
- Administration of study intervention will occur according to the EDR;
- In order to standardize the conditions on PK sampling days, all participants will be required to refrain from lying down (except when required for BP, pulse rate, and ECG measurements), eating, and drinking beverages other than water during the **first 4 hours after dosing**.

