**TABLE 8. URINE PK PARAMETERS TO BE SUMMARIZED DESCRIPTIVELY**

Parameter	Summary Statistics
Ae tau , Ae tau % and CL r	N, arithmetic mean, median, %CV, SD, min, max, geometric mean and geometric %CV.

- **Part 1 (Single, Escalating Doses):**
- Plasma concentrations of PF-07202954 will be descriptively summarized and plotted by nominal PK sampling time and dose.

- The plasma PK parameters  $AUC_{inf}$ ,  $C_{max}$ ,  $AUC_{last}$ ,  $T_{max}$ ,  $T_{lag}$ ,  $CL/F$ ,  $V_z/F$ , and  $t_{1/2}$  will be summarized descriptively by dose;

[REDACTED]

[REDACTED]

- **Part 2 (Repeated, Escalating Doses):**

- Plasma concentrations of PF-07202954 will be descriptively summarized and plotted by nominal PK sampling time, day, and dose;
- The plasma PK parameters  $AUC_{tau}$ ,  $C_{max}$ ,  $T_{max}$ ,  $T_{lag}$ ,  $t_{1/2}$ ,  $C_{min}$ ,  $C_{av}$ ,  $PTR$ ,  $CL/F$ ,  $V_z/F$ ,  $R_{ac,AUC_{tau}}$ , and  $R_{ac,Cmax}$ , and the urine PK parameters  $Ae_{tau}$ ,  $Ae_{tau}\%$ , and  $CL_r$  will be summarized descriptively by dose and day as applicable;

[figure not shown]
[figure not shown]
[REDACTED]

- Median morning trough (predose) plasma concentrations will be plotted by day (all doses on the same plot) in order to assess the attainment of steady state.
- **Part 3 (Single-Dose Food Effect, if conducted):** To compare PF-07202954 exposures following high-fat/high-caloric meal (Test) versus following an overnight fast (Reference) natural log-transformed  $C_{max}$ ,  $AUC_{last}$ , and  $AUC_{inf}$  (if data permit) will be analyzed using a mixed effects ANOVA described in Section 5.2. Estimates of the adjusted mean differences (Test-Reference) and the corresponding 90% CIs will be obtained from the model. The adjusted mean differences and 90% CIs for the differences will be exponentiated to provide estimates of the ratio of adjusted geometric means (Test/Reference) and 90% CIs for the ratios.

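### Part 3 permits free water around dosing in the fed period but not in the fasted period, so the food-effect ratio cannot separate the meal from the water rule

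*Protocol*

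**What the plan says.** **Fed dosing.** A general bullet in Protocol Section 5.3.1 reads: "Water may be consumed *without restrictions* both prior to *and* after study intervention administration when dosing occurs following a standard morning meal (or high-fat/high-caloric meal"). It names the high-fat/high-caloric meal, and the Part 3 fed-state bullets later in the section add no limit, so it governs the Part 3 Test period.

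**Fasted dosing.** The Part 3 fasted-state bullet reads: "water is permitted until 1 hour prior to dosing and water may be consumed without restriction beginning at 1 hour after dosing".

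**Dosing water.** Section 6.1.1 treats the two states alike: "In all cases, investigator site personnel will administer study intervention during each period with ambient temperature water to a total volume of approximately 240 mL". It adds a rinse allowance, "Additional water (up to 120 mL) may be consumed by the participants", with such instances documented in source. Its standardisation rule for the first 4 hours after dosing covers lying down, "eating, and drinking beverages other than water during the" that window, so it does not limit water.

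**Analysis.** Under SAP Section 6.2 the log-transformed Cmax, AUClast and AUCinf "will be analyzed using a mixed effects ANOVA described in Section 5.2". For Part 3 that model has sequence, period and treatment as fixed effects and participant within sequence as random. Protocol Section 9.4.3.2 describes a simpler model with treatment fixed, participant random and period optional. Neither has a term for water, and SoA Table D has no entry for recording it.

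**The concern.** The primary objective of Part 3 is the effect of a high-fat/high-caloric meal on plasma PK. A within-participant comparison isolates the meal only if the other conditions around dosing are the same in both periods. Here one of them, the water permitted within an hour of dosing, switches with the meal. The plan fixes the water swallowed with the dose, which suggests that fluid at dosing was thought worth controlling, but it controls the surrounding water in one period only and gives no reason for the difference.

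At stake is what the Test/Reference ratio means. As written, it compares a meal plus permitted free water with a fast plus restricted water. The protocol expects food to have minimal impact (Sections 2.2.3 and 4.2.5), so the true meal effect may lie near 1.0, where a small nuisance shift is hardest to tell from a real meal effect.

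**Working it through.** **1. The plan's own figure.** Protocol Table 6 gives the only numbers for the Part 3 contrast: the probable 90% CI, with 80% coverage probability, for a true ratio of 1.0. For a two-period crossover with n participants and within-participant log-scale SD s, the limits are exp(±h), where

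h = t(0.95, n−2) × s × √(2/n) × √(χ²(0.80, n−2)/(n−2)).

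- n = 12, s = 0.24: 1.812 × 0.24 × 0.408 × 1.159 = 0.206, giving 0.81 to 1.23, as in Table 6.
- n = 8, s = 0.24: 1.943 × 0.24 × 0.5 × 1.194 = 0.278, giving 0.76 to 1.32, as in Table 6.

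All nine cells reproduce to two decimals, so the precision statement is sound. The point below changes none of these figures.

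**2. The conditions side by side.**

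| Condition (Part 3) | Fasted (Reference) | Fed (Test) |
|---|---|---|
| Dosing water (6.1.1) | about 240 mL | about 240 mL |
| Rinse water (6.1.1) | up to 120 mL | up to 120 mL |
| Free water, 1 h before to dosing (5.3.1) | none | unrestricted |
| Free water, dosing to 1 h after (5.3.1) | none | unrestricted |
| Free water later than 1 h after (5.3.1) | unrestricted | unrestricted |

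The difference is therefore confined to optional water in a window of about 2 hours, and it is a difference in what is permitted. Actual intake is neither fixed nor recorded.

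**3. What the model can estimate.** Write the log exposure in a given period as the model's sequence, period and participant terms plus θM × M + θW × W, where M = 1 for the meal and W = 1 for free-water permission. By protocol, W = M in every period of every participant, so only θM + θW is estimable. Randomised order and the period and sequence terms cannot split the sum. A larger n narrows the interval around exp(θM + θW) and does not move it towards exp(θM).

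**4. Size.** The documents give no effect of water on exposure, so θW cannot be derived. For illustration only, assume that the true meal effect is 1.0, that s = 0.24, and that water alone multiplies the ratio by the value in the first column. The Table 6 interval is then multiplied by that value:

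| Assumed shift from water | n = 8 | n = 12 |
|---|---|---|
| 1.00 | 0.76–1.32 | 0.81–1.23 |
| 1.05 | 0.79–1.39 | 0.85–1.29 |
| 1.10 | 0.83–1.45 | 0.90–1.35 |
| 1.20 | 0.91–1.59 | 0.98–1.47 |

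The direction is also unknown, and a shift below 1 would move the interval down instead.

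**5. Part 1, Period 4.** If Period 4 is used to explore food, Section 5.3.1 sends dosing to the Part 3 conditions, and the comparison is with earlier standard-meal Periods in the same cohort (Section 4.2.2; Table 5, note b). Those earlier Periods had free water. A fasted Period 4 therefore differs from them in permitted water as well as in food. A high-fat Period 4 currently matches them on water, and any change made for Part 3 should not break that match.

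**The case against.** The strongest reply is that the effect is probably small and that the plan says why. Section 2.2.3 calls solubility high relative to the dose range and the risk of solubility-limited absorption low, and names efflux transport as the likelier source of non-linear PK. Section 4.2.5 expects minimal food impact at doses up to 1500 mg. Dosing water is equal, the remaining difference is optional drinking, and about 20 minutes of the window is spent eating. Part 3 is also conditional, tests no hypothesis and sets no equivalence margin. Free water with food may even be closer to expected use. All of this stands as a limit on severity. It does not restore the separation of meal and water, and the protocol does not present the difference as deliberate.

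Two stronger readings are tempting, and the documents support neither.

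- **That solubility capacity shows a material effect.** Section 2.2.3 says that intestinal solubility, fasted and fed, "was observed to be 0.7 mg/mL and 1.2 mg/mL, respectively". So 240 mL holds 240 × 0.7 = 168 mg or 240 × 1.2 = 288 mg, against Table 3 doses of 300 to 1000 mg. But Table 3 lists Part 1 doses and the Part 3 dose is not fixed. In simulated gastric fluid (>27 mg/mL) the same volume holds more than 240 × 27 = 6,480 mg, over three times the 2000 mg ceiling. A static capacity figure does not measure absorption.
- **That free water inflates variability beyond the sizing assumption.** Section 9.2 sets the Part 3 sample size from variability seen in Part 1, where standard-meal dosing already allows free water. Any such variability would already be in that estimate.

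**Conclusion.** The point holds as a minor design flaw. Permitted water within an hour of dosing is fully aligned with treatment in every Part 3 participant. Nothing in the protocol or SAP equalises it, records it or adjusts for it, so the primary ratio estimates the meal together with the water rule.

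Size and direction cannot be set from the documents, and the shift may be negligible. The conclusion rests on reading the general free-water bullet as governing Part 3 fed dosing, which its explicit mention of the high-fat/high-caloric meal supports. A reader might infer that the Part 3 result would be invalid, or that actual intake will differ materially. The documents show only a difference in permission and do not support either inference.

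**What to change.** - For the two Part 3 periods only, apply one water rule in Section 5.3.1: no water from 1 h before to 1 h after dosing, other than the dosing and rinse water and any fluid that is part of the test meal.
- Keep free water for standard-meal dosing in Parts 1 and 2 and for any high-fat dosing in Part 1 Period 4, so that it still matches the earlier standard-meal Periods. Reword the Period 4 cross-reference to the Part 3 conditions to carve this out. Simply confining free water to standard meals would create a new mismatch there.
- State that a fasted Period 4 differs from earlier standard-meal Periods in permitted water as well as in food, so that an exploratory result is read accordingly.

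**Cost.** A few sentences, with no added procedure, data or participants. Participants go about 2 h without extra water in the Part 3 fed period. One residual difference follows: high-fat dosing in Part 1 Period 4 and in Part 3 would then run under different water rules, which matters only if the two are compared directly.
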